12.1 Stratification Factors

No stratifications are planned in either phase of the study.

12.2 Analysis of Secondary Endpoints

Toxicity will be graded according to the NCI CTC version 4.03 and relationship to study drug will be assessed. Toxicities will be tabulated by dose of calcitriol. All patients who receive study drug will be considered evaluable for toxicity.

Objective tumor response will be judged by monthly physical exam and radiographic evaluation which will be done q12 weeks. Patients will be considered evaluable for tumor response if they have at least two post-baseline tumor assessments at least 4 weeks apart, received study medication for 8 weeks or if they have evidence of disease progression.

Analysis of the correlative studies in section 8.0 will be descriptive.

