1. OBJECTIVES

Primary Objective

To estimate the PSA response rate with the use of ketoconazole (400mg QD + hydrocortisone 20mg AM, 10 mg PM) + calcitriol (10mcg QD X3 weekly) among men with CRPC in whom disease has progressed despite abiraterone

Secondary Objectives

Describe objective tumor responses to the combination of oral calcitriol and ketoconazole and hydrocortisone-among patients with measurable disease using modified RECIST1.1 criteria.

Determine toxicities, and tolerability of oral calcitriol combination with daily oral ketoconazole, and hydrocortisone in this patient population.

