3.1 Inclusion Criteria

For inclusion in the trial, a patient must fulfill all of the following criteria:

1. ≥ 18 years of age. The effects of ketoconazole and high-dose calcitriol have not been studied adequately in patients < 18 years of age and prostate cancer has not been described in children.

2. Histologically or cytologically confirmed adenocarcinoma consistent clinically with androgen Independent prostate cancer
3. Measurable disease with elevated PSA or evaluable disease (PSA elevation will constitute evaluable disease).
4. No cytotoxic chemotherapy for extensive disease prior to study entry will be allowed; given the recent data regarding the role of docetaxel + ADT in patients beginning ADT for advanced disease, such “adjuvant chemotherapy will be allowed (no more than 6 cycles) retinoids, vitamin D analogues, PPAR γ agonists or antagonists, antiandrogens, progestational agents, estrogens, PC-SPEs, LHRH-analogues, vaccines, cytokines will not be considered “cytotoxics.” Patients who have previously received ketoconazole + glucocorticoids will **NOT** be eligible for this trial.
5. Patients who have received antiandrogens or progestational agents as therapy for prostate cancer must discontinue therapy and demonstrate a rising PSA \geq 28 days following discontinuation (antiandrogen withdrawal – AAW) (\geq 42 days for bicalutamide or nilutamide). Patients who receive megestrol acetate as therapy for “hot flashes” at a dose of \leq 40mg per day may continue this therapy during this trial. The dose of the megestrol acetate should not be changed during protocol treatment. Patients undergoing androgen deprivation using LHRH analogues must continue such agents or undergo orchiectomy to maintain castrate levels of testosterone.
6. Patients must have prostate cancer that is advanced or recurrent.
7. Patients should not have received any chemotherapy or investigational agents for at least 28 days before entering the study.
8. Eastern Clinical Oncology Group performance status 0 or 1
9. Life expectancy >3 months.
10. Patients must have normal organ and marrow function as defined below: patients may be transfused to meet with these parameters at the physician’s discretion.
 - leukocytes: \geq 3,000/ μ l
 - hemoglobin: \geq 8 g/dl
 - absolute neutrophil count (ANC): \geq 1,500/ μ l
 - platelets: \geq 75,000/ μ l
 - total bilirubin: within normal institutional limit
 - AST/ALT: \leq 2.5 X institutional upper limit of normal
 - creatinine: \leq 2mg/dL

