7.0 STUDY CALENDAR

Baseline evaluations are to be conducted within 28 days prior to start of protocol therapy. Radiographs must be done within 6 weeks of entering the study.

		Cycle 1				Cycle 2				Cycle 3				Cycles 4+	Off Study
	Pre-Study (-28 to -1 days)	Wk 1	Wk 2	Wk 3	Wk 4	Wk 5	Wk 6	Wk 7	Wk 8	Wk 9	Wk 10	Wk 11	Wk 12		
Ketoconazole		X	X	X	X	X	X	X	X	X	X	X	X	Weekly	
Calcitriol		X	X	X	X	X	X	X	X	X	X	X	X	Weekly	
Hydrocortisone		X	X	X	X	X	X	X	X	X	X	X	X	Weekly	
Informed consent	X														
Demographics	X														
Concurrent meds	X					X				X				Every 4 wks	
Medical history	X													Every 4 wks	X
Physical exam, Vital Signs, Weight	X					X				X				Every 4 wks	X
CBC w/diff, plts	X					X				X				Every 4 wks	X
Serum chemistry ^a	X					X				X				Every 4 wks	X
Adverse event evaluation						X				X				Every 4 wks	
Performance status	X					X				X				Every 4 wks	X
PSA	X					X				X				Every 4 wks	
Tumor measurements	X	Tumor measurements are repeated every 4-12 weeks (measurable disease). Documentation (radiologic) must be provided for patients removed from study for progressive disease.													X ^c
Radiologic evaluation ^b	X	Radiologic measurements should be performed every 12 weeks from the start of calcitriol													X ^c

Ketoconazole: 400 mg given TID starting D 1 (except if participating in the PK portion begin day 4)

Calcitriol: 10 mcg; Calcitriol will be given for 3 consecutive days starting the 1st day of each week, day 1,2,3,8,9,10,15,16,17

Hydrocortisone: will be given 20mg AM, 10mg PM in the evening starting the day before the first dose of calcitriol

a--Alkaline phosphatase, total bilirubin, LDH, total protein, SGOT(AST), SGPT(ALT) will be obtained monthly. Albumin, Bicarbonate, BUN, calcium, chloride, creatinine, glucose, total protein, and phosphorous will be obtained monthly.

b- Every 12 weeks in patients with measurable disease. Every 12 weeks in the absence of measurable disease.

c- If partial or complete response are assessed, repeat in 1 month for confirmation. Longer intervals as determined by the study protocol may also be appropriate.

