5 REPORTING OF RESULTS

All patients included in the study must be assessed for response to treatment, even if there are major protocol treatment deviations or if they are ineligible. Each patient will be assigned one of the following categories: 1) complete response, 2) partial response, 3) stable disease, 4) progressive disease, 5) early death from malignant disease, 6) early death from toxicity, 7) early death because of other cause, or 9) unknown (not assessable, insufficient data). (*Note:* By arbitrary convention, category 9 usually designates the "unknown" status of any type of data in a clinical database.)

All of the patients who met the eligibility criteria should be included in the main analysis of the response rate. Patients in response categories 4-9 should be considered as failing to respond to treatment (disease progression). Thus, an incorrect treatment schedule or drug administration does not result in exclusion from the analysis of the response rate. Precise definitions for categories 4-9 will be protocol specific.

All conclusions should be based on all eligible patients.

Subanalyses may then be performed on the basis of a subset of patients, excluding those for whom major protocol deviations have been identified (e.g., early death due to other reasons, early discontinuation of treatment, major protocol violations, etc). However, these subanalyses may not serve as the basis for drawing conclusions concerning treatment efficacy, and the reasons for excluding patients from the analysis should be clearly reported. The 95% confidence intervals should be provided.

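### Section 12.2 drops early stoppers from the objective response rate, while Appendix B counts them as non-responders

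*Combined protocol and SAP*

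**What the plan says.** Section 12.2 (Analysis of Secondary Endpoints) first gives the method: "Objective tumor response will be judged by monthly physical exam and radiographic evaluation which will be done q12 weeks". It then makes patients "evaluable for tumor response if they have at least two post-baseline tumor assessments at least 4 weeks apart, received study medication for 8 weeks", and the sentence closes by adding progression: "received study medication for 8 weeks or if they have evidence of disease progression". It does not say how men outside the rule are reported, and it does not mention measurable disease.

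Other sections bear on the same denominator:

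- **Section 1** describes objective response "among patients with measurable disease". Section 8.1 likewise assesses complete and partial response in men with measurable disease, asks for confirmation at least 4 weeks later, and refers to Appendix B for detail.
- **Section 3.1, item 3** admits men without measurable disease: "PSA elevation will constitute evaluable disease".
- **Section 7.0** (study calendar) places on-study physical exams in weeks 5 and 9 and then every 4 weeks. Tumor measurements in measurable disease come at intervals of 4 to 12 weeks. For imaging, "Radiologic measurements should be performed every 12 weeks from the start of calcitriol".
- **Appendix B, section 5** puts every patient who met the eligibility criteria into the main analysis of response rate. "Patients in response categories 4-9 should be considered as failing to respond to treatment"; these categories run from progressive disease, through early deaths, to unknown or not assessable. Analyses that leave out early discontinuations are permitted only as subanalyses and cannot support efficacy conclusions. 95% confidence intervals are expected.

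**The concern.** The protocol foresees early exits. Section 5.2 takes men off study for drug-related grade 3 or 4 non-hematopoietic toxicity, with stated exceptions. A man with measurable disease who leaves this way before 8 weeks can fail every part of the 12.2 rule and drop out of the denominator. Appendix B keeps the same man in and counts him as a failure.

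So one document gives two response rates for the same data. The rate under 12.2 favors the regimen, because the men removed include those who could not tolerate it. With 15 patients expected, and only some of them with measurable disease, one or two such men change the reported rate visibly. As the text stands, the choice between the two rates could be made after the data are seen.

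**Working it through.** **1. The plan's own figures.** The documents state no target rate, sample size or power for objective response. The only operating figures (section 12.0) belong to the PSA endpoint: type I error 10%, early stopping under the null 39%, power 93%. Exact enumeration over the 25 equally weighted combinations of stage 1 size (7–11) and total size (13–17) declares activity for more than 2 responses in 13–14 men or more than 3 in 15–17. It gives 9.7%, 39.2% and 93.5%. The tumor-response rule does not enter these figures.

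**2. Does an early stopper meet the rule?** Take a man with measurable disease, under 8 weeks of drug, no progression, and no two assessments 4 weeks apart. The list has only one connective, so it can be read in more than one way:

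| Reading of the list | Evaluable? |
|---|---|
| Any one of the three conditions | No |
| Both of the first two, or progression | No |
| The first, plus either of the other two | No |

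He is excluded on every reading.

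**3. Does the schedule rescue him?** Not normally. The exams in weeks 5 and 9 are 4 weeks apart, but the second falls after 8 weeks. Tumor measurements at the shortest interval would fall at weeks 4 and 8, so only one is planned before week 8. The calendar also has an off-study assessment. It helps only a man who stops late in the window and has that assessment at least 4 weeks after an earlier one.

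**4. Direction.** Let x be the confirmed responders, M the eligible men with measurable disease, and T the early stoppers among them whom 12.2 drops. Section 8.1 requires confirmation at least 4 weeks later. A man without two assessments 4 weeks apart therefore cannot be a confirmed responder, and x is the same under both rules.

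- Appendix B: x/M
- Section 12.2: x/(M − T)
- Ratio: M/(M − T), which exceeds 1 whenever T ≥ 1

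**5. Size.** M and T are not in the documents. Assume M = 6, 8 or 10 of the 15 expected patients, T = 1 to 3, and x = 2.

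| M | Appendix B rate | T = 1 | T = 2 | T = 3 |
|---|---|---|---|---|
| 6 | 2/6 = 33.3% | 2/5 = 40.0% (×1.20) | 2/4 = 50.0% (×1.50) | 2/3 = 66.7% (×2.00) |
| 8 | 2/8 = 25.0% | 2/7 = 28.6% (×1.14) | 2/6 = 33.3% (×1.33) | 2/5 = 40.0% (×1.60) |
| 10 | 2/10 = 20.0% | 2/9 = 22.2% (×1.11) | 2/8 = 25.0% (×1.25) | 2/7 = 28.6% (×1.43) |

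For M = 8 and T = 2, the exact (Clopper-Pearson) 95% intervals are 3.2–65.1% for 2/8 and 4.3–77.7% for 2/6.

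**The case against.** **Appendix B is general guidance, and 12.2 is the trial's own rule.** Appendix B, section 3.2.3, leaves the conditions for nonevaluability to each protocol, so 12.2 may define them. That much stands. But section 5 of the same appendix then counts non-assessable patients as failures. Defining the category does not remove its members from the denominator, and no order of precedence is stated.

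**The endpoint is descriptive and the trial is small.** This also stands. No test or decision rule depends on objective response, and the intervals above are much wider than the shift. If every man's response category is reported, as Appendix B asks, a reader can rebuild either rate, so it would go too far to call the result uninterpretable. Still, the shift has a known direction and is avoidable, which sampling error is not.

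Three stronger readings are tempting, and the documents do not support them:

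- **Men with PSA elevation only are in the denominator.** Taken alone, 12.2 has no measurable-disease condition. With 15 men and 2 early stoppers it would give 2/13 = 15.4%. Sections 1 and 8.1 already restrict objective response to measurable disease; 12.2 merely fails to repeat this.
- **Eight weeks of drug wrongly counts men with no scan.** The first scheduled scan is at 12 weeks, but this reading requires that any one condition suffices. Monthly exams also count as assessment, although Appendix B, section 2.2.1, limits that to superficial lesions. In any case, keeping an eligible man with measurable disease and no scan as a non-responder is what Appendix B requires.
- **Men with stable disease must wait until week 24 for a second assessment.** This treats the 12-weekly radiographs as the only assessments and ignores the monthly exams and the 4- to 12-week measurement interval.

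**Conclusion.** Section 12.2 and Appendix B, section 5, conflict on who is counted for objective response. The conflict concerns men with measurable disease who stop before 8 weeks without progression and without two assessments at least 4 weeks apart. It holds on every reading of the ambiguous sentence.

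The direction is certain given the confirmation requirement: if there is at least one responder and at least one such man, the 12.2 rate is the higher. The size rests on assumption. It is a factor of 1.11 to 2.0 for 6 to 10 men with measurable disease and 1 to 3 early stoppers. The missing measurable-disease condition and the unclear connective are drafting faults to repair in the same edit. The change should be made, but it concerns a secondary, descriptive endpoint. The PSA decision rule and the sample size are untouched.

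**What to change.** Replace the evaluability sentence in section 12.2 with:

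> Objective response is reported for all eligible patients with measurable disease at baseline who received any study drug. Patients without adequate post-baseline tumor assessment, including early stoppers, are counted as non-responders. An exact 95% confidence interval is given. Any evaluable-only rate is a subanalysis.

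This removes the ambiguous list, states the population of sections 1 and 8.1, and follows Appendix B on failures and intervals. The condition of having received study drug is slightly narrower than Appendix B, which counts all eligible patients; the number of eligible men never treated should be reported alongside.

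The cost is a short text change, with no new data, visits or patients. The reported rate may be lower than one that omits early stoppers: 25% rather than 33% in the illustration with M = 8 and T = 2.

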13.0 TRIAL MANAGEMENT

13.1 Audits and Inspections

Audits and data management will be overseen by the ISCI CTO

13.2 Changes to the Protocol

If it is necessary for the trial protocol to be amended, the amendment or a new version of the trial protocol must be notified to or approved by the IRB. If a protocol amendment requires a change to the Informed Consent Form the IRB will be notified. Approval of the revised Written Informed Consent Form by the IRB is required before the revised form is used.

13.3 Ethics

The principal investigator is responsible for providing the IRB with reports of any SAEs from any other trial conducted with the investigational product. The trial will be performed in accordance with Good Clinical Practice.

Amendments, reporting deviations, AE reports will be reported to the Institutional Review Board.

13.4 Emergency Procedures

13.4.1 Procedures in Case of a Medical Emergency

The principal investigator is responsible for ensuring that procedures and expertise are available to handle medical emergencies during the study.

13.4.2 Procedures in Case of Pregnancy

Pregnancy itself is not regarded as an AE unless there is a suspicion that the investigational product under study may have interfered with the effectiveness of a contraceptive medication. However, the outcome of all pregnancies (spontaneous miscarriage, elective termination, normal birth, or congenital abnormality) must be followed up and documented even if the patient was discontinued from the study.

All reports of congenital abnormalities/birth defects are SAEs. Spontaneous miscarriages should also be reported and handled as SAEs. Elective abortions without complications should not be handled as AEs.

13.5 Data Accessibility

Data are stored in locked files in Clinical Research Services (CRS), access to which is limited to authorized CRS personnel only. Research data are also maintained in the ISCI clinical trials data base and secured, password protected and not connected to a network.

APPENDIX A

Performance Status Criteria

ECOG Performance Status Scale		Karnofsky Performance Scale	
Grade	Descriptions	Percent	Description
0	Normal activity. Fully active, able to carry on all pre-disease performance without restriction.	100	Normal, no complaints, no evidence of disease.
		90	Able to carry on normal activity; minor signs or symptoms of disease.
1	Symptoms, but ambulatory. Restricted in physically strenuous activity, but ambulatory and able to carry out work of a light or sedentary nature (e.g., light housework, office work).	80	Normal activity with effort; some signs or symptoms of disease.
		70	Cares for self, unable to carry on normal activity or to do active work.
2	In bed <50% of the time. Ambulatory and capable of all self-care, but unable to carry out any work activities. Up and about more than 50% of waking hours.	60	Requires occasional assistance, but is able to care for most of his/her needs.
		50	Requires considerable assistance and frequent medical care.
3	In bed >50% of the time. Capable of only limited self-care, confined to bed or chair more than 50% of waking hours.	40	Disabled, requires special care and assistance.
		30	Severely disabled, hospitalization indicated. Death not imminent.
4	100% bedridden. Completely disabled. Cannot carry on any self-care. Totally confined to bed or chair.	20	Very sick, hospitalization indicated. Death not imminent.
		10	Moribund, fatal processes progressing rapidly.
5	Dead.	0	Dead.

APPENDIX B

Response Criteria

1 Introduction

The introduction explores the definitions, assumptions, and purposes of tumor response criteria. Below, guidelines that are offered may lead to more uniform reporting of outcomes of clinical trials. Note that, although single investigational agents are discussed, the principles are the same for drug combinations, non-investigational agents, or approaches that do not involve drugs.

Tumor response associated with the administration of anticancer agents can be evaluated for at least three important purposes that are conceptually distinct:

- Tumor response as a prospective end point in early clinical trials. In this situation, objective tumor response is employed to determine whether the agent/regimen demonstrates sufficiently encouraging results to warrant further testing. These trials are typically Phase II trials of investigational agents/regimens (see Section 1.2), and it is for use in this precise context that these guidelines have been developed.
- Tumor response as a prospective end point in more definitive clinical trials designed to provide an estimate of benefit for a specific cohort of patients. These trials are often randomized comparative trials or single-arm comparisons of combinations of agents with historical control subjects. In this setting, objective tumor response is used as a surrogate end point for other measures of clinical benefit, including time to event (death or disease progression) and symptom control (see Section 1.3).
- Tumor response as a guide for the clinician and patient or study subject in decisions about continuation of current therapy. This purpose is applicable both to clinical trials and to routine practice (see Section 1.1), but use in the context of decisions regarding continuation of therapy is not the primary focus of this document.

However, in day-to-day usage, the distinction among these uses of the term "tumor response" can easily be missed, unless an effort is made to be explicit. When these differences are ignored, inappropriate methodology may be used and incorrect conclusions may result.

1.1 Response outcomes in daily clinical practice of oncology

The evaluation of tumor response in the daily clinical practice of oncology may not be performed according to predefined criteria. It may, rather, be based on a subjective medical judgment that results from clinical and laboratory data that are used to assess the treatment benefit for the patient. The defined criteria developed further in this document are not necessarily applicable or complete in such a context. It might be appropriate to

make a distinction between "clinical improvement" and "objective tumor response" in routine patient management outside the context of a clinical trial.

1.2 Response outcomes in uncontrolled trials as a guide to further testing of a new therapy

"Observed response rate" is often employed in single-arm studies as a "screen" for new anticancer agents that warrant further testing. Related outcomes, such as response duration or proportion of patients with complete response, are sometimes employed in a similar fashion. The utilization of a response rate in this way is not encumbered by an implied assumption about the therapeutic benefit of such responses but rather implies some degree of biologic antitumor activity of the investigated agent.

For certain types of agents (ie, cytotoxic drugs and hormones), experience has demonstrated that objective antitumor responses observed at a rate higher than would have been expected to occur spontaneously can be useful in selecting anticancer agents for further study. Some agents selected in this way have eventually proven to be clinically useful. Furthermore, criteria for "screening" new agents in this way can be modified by accumulated experience and eventually validated in terms of the efficiency by which agents so screened are shown to be of clinical value by later, more definitive, trials.

In most circumstances, however, a new agent achieving a response rate determined *a priori* to be sufficiently interesting to warrant further testing may not prove to be an effective treatment for the studied disease in subsequent randomized Phase III trials. Random variables and selection biases, both known and unknown, can have an overwhelming effect in small, uncontrolled trials. These trials are an efficient and economic step for initial evaluation of the activity of a new agent or combination in a given disease setting. However, many such trials are performed, and the proportion that will provide false-positive results is necessarily substantial. In many circumstances, it would be appropriate to perform a second small confirmatory trial before initiating large resource-intensive Phase III trials.

Sometimes, several new therapeutic approaches are studied in a randomized Phase II trial. The purpose of randomization in this setting, as in Phase III studies, is to minimize the impact of random imbalances in prognostic variables. However, randomized Phase II studies are, by definition, not intended to provide an adequately powered comparison between arms (regimens). Rather, the goal is simply to identify one or more arms for further testing, and the sample size is chosen so to provide reasonable confidence that a truly inferior arm is not likely to be selected. Therefore, reporting the results of such randomized Phase II trials should not imply statistical comparisons between treatment arms.

